#### **D4. Maximizing the Intervention - Programming, and Usability Testing**

As noted in our task list, the majority of the effort in this project will be devoted to the randomized trial, with recruitment, retention, data collection, and analyses being the major tasks. We have begun to develop conceptual mock-ups of the Refer2Quit portal. *The goal of the referral portal is to be used within the flow of dental care, so the portal must be highly accessible and require minimal data entry. Currently, we plan to only ask hygienists to log into the system and enter the patients email address; that is the only data entry and should take less than one minute.* However, implementing the Internet-delivered intervention will require some refinement of both the content and programming. As noted, content upgrades are critical to engagement and we plan to continuously improve both the patient and provider sites as the study progresses using the following phases:

[figure not shown]
1. Hardware and software for programming. The technological foundation of the intervention will be updated as the Internet evolves. Under the direction of [name], the programming will be developed and maintained by the UAB Continuing Medical Education (UAB CME) web development lab. The UAB CME web lab has four graduate level computer science students at all times and two half-time graphic designers. Currently, our study team uses Windows NT server; Active Server Pages (ASP) server application; Ultra Dev 4; Adobe Photoshop; and Oracle databases for data collection. We will alpha-test the program using multiple web browsers and various bandwidths to avoid cross-platform issues in accessing the intervention. The encryption of content is critical and needs of HIPAA compliance will be carefully tested.
2. Usability Assessment. Volunteers recruited from dentist practices in the Birmingham area will perform beta-testing of the potential human-computer interface to confirm that the system is understandable and easily used. To avoid contamination, we will not recruit these pilot testers into the main RCT. We will beta-test the website with a series of individual patient and hygienist interviews while reviewing the modules. We will use "Think Aloud" protocols detailed by Kushniruk as follows: while the participants are reviewing the content, the user will be asked to vocalize thoughts, feelings, and opinions while interacting with the program. Think Aloud allows you to understand how the user approaches the interface and what considerations the user keeps in mind when using the interface. Participants will complete a rating instrument including questions addressing the acceptability, accuracy, ease of use, and satisfaction with the program. We will use these data to refine the program.

#### **D5. Recruitment and Randomization Phase 1: Dental Practices**

To conduct the RCT, we will recruit dental practices. We plan to recruit 80 general dentistry practices (40 total practices per arm) from the *Dental PBRN* to participate using recruitment methods developed in DTC.Net and our other Internet-delivered trials (see Table 2) each of which have nearly 200 practices participating.

**Inclusion Criteria:** Our primary inclusion criteria are community-based practices with Internet access available in the office seeing an average of five or more smokers in a week. Because access to the Internet by health providers continues to increase, when this study is conducted, access to broadband Internet in dentist offices will be approaching universality. Based on our prior experience, enrollment of practices in these studies is complex and somewhat easier if the number of providers in the practice is lower. *We will exclude practices that have ongoing computer-based smoking cessation programs for patients.*

Recruitment and consent to cluster-randomized trials is often layered, especially if the intervention is delivered at several layers. Thus, based on prior methods, we have designed a stepped recruitment and consent procedure. **Provider Recruitment** will follow 5 steps:

In our current Dental PBRN study, DTC.Net, we recruited 190 practices from four states. In the NHLBI-funded MI-Plus study, we recruited 210 providers from Alabama and Mississippi. Using a combination of mass mailings with stepped follow-up and a run-in phase, we have been successful in recruiting and retaining large number of provider practices (follow-up currently 76% in DTC.Net). We do not envision excessive difficulties in recruiting and retaining these Internet-ready dental practices.

Principal Investigator/Program Director (Last, First, Middle): DPBRN c/o [name]

1. Initial Interest Survey - For HI-QUIT, we will send an initial interest letter that will identify the study as access to a provider information portal for smoking cessation and a free referral resource for patients. Dental providers will be informed that evaluation includes monitoring their use of the website, patient's use of website, and agreement for staff to distribute exit card surveys to patients as they leave their visit. The letter will be accompanied by a form for practices to express interest and initial eligibility.

2. Initial Practice Consent - Interested practices will be sent a more-detailed package with materials explaining the study, and an initial consent. Because the clinical microsystem is the ultimate target of HI-QUIT, consent for this project is complex. The intervention is designed to be integrated into the workflow of practice, and we hope dentists and hygienists will participate along with their patients. We will ask the provider who completed the interest card to discuss the study with all providers in the practice to reach consensus. An initial consent is signed by the interest card provider.

3) Provider Agreement to be Contacted – After the initial consent is signed, the initial consent provider will be asked to assign a contact person (staff member) at the practice. The staff member will be asked to use the data collection form to collect names and emails of all providers (hygienists, dental assistants, dentists) who agree to be contacted with information about the website. We will not limit the number of providers who are eligible to participate, but expect that not all providers in all practices will be actively involved.

4) Run-in Data Collection - Once the initial consent and agreement to be contacted forms are returned, interested practices are asked to complete a run-in phase where baseline patient and practice data are collected and returned. Our recruitment coordinators will call the contact person at the practice who is responsible for data collection to answer any questions.

5) Individual Provider Consent - After the run-in phase is completed, providers will begin to access the website, and begin to refer patients to the intervention. We will broadcast emails to all those who agree to be contacted. Each of these marketing emails will include instructions for opting out. Before accessing the content, providers will read a consent and will have to actively agree by completing check-boxes to 1) allow us to track their activity on the website, 2) allow us to continue to email them with updates, 3) refer patients to the patient intervention. Randomization is described below. Patient recruitment is in Section D6.

**Randomization** - We will use an online randomization algorithm developed by [name]. Once providers review the recruitment and consent information online, those that agree to participate will proceed to update their contact information and then click on a link [I AGREE TO PARTICIPATE]. Once they click on this link, a program on the server will randomize their practice to the control or intervention arms in blocks of six to assure roughly equal numbers. Thus, the first provider who logs on will determine the randomization status for all providers and staff within the entire practice. This ensures that the level of randomization is the clinical microsystem (dental practice).

**Anticipating attrition** – Although data are not complete for follow-up in DTC.Net, we currently have data from 143 of 190 randomized practices (76%) and anticipate a final participation rate at follow-up of 80%. Using these numbers, we plan to recruit 100 practices to the “interested” pool, to obtain 80 practices to be randomized. For power calculations, we have estimated that a range from 30 to 40 practices per arm will complete follow-up data collection. If the practices withdraw from the study prematurely, we will retain their data as for an “intention to treat” analysis. We will compare practices that withdraw with those that do not.

6. Recruitment Phase 2: Patient Recruitment for Outcomes Assessment - Patients will be recruited to participate in the study in two ways, as determined by our analysis plan. First, patients will be recruited to assess providers using brief exit card surveys completed as they are discharged from their clinic appointment. Second, patients will be enrolled as they login to the patient website.

**Patient Recruitment Part 1: (Exit Card Surveys)** - For *Hypothesis 1* (Processes of Care – including the proportion of patients who are referred to self-management resources will be greater in HI-QUIT practices compared with control practices) we need a measure of provider performance. Provider reports of smoking counseling over-estimate and chart abstraction under-estimates performance. Patient reports of provider behavior have also been used. The Health Plan Employer Data and Information Set (HEDIS) performance measurement has adopted patient-report of provider tobacco cessation advice using phone

Principal Investigator/Program Director (Last, First, Middle): DPBRN c/o [name]

interviews. However, these delayed reports of provider performance may suffer from recall bias due to time elapsed from the patient visit to the time of follow-up assessment. Immediate exit interviews for smoking cessation have been found to correlate with audiotapes.

In DTC.Net, we have developed and evaluated patient-reported provider performance measures that are completed and collected and the time of the visit on “Exit Cards.” These patient Exit Cards – brief surveys completed by patients at the end of their appointment – were developed using principles of ecological momentary assessment (EMA). EMA is a method used in health behavior and more recently in health services research to overcome limitations of traditional self-report assessments.

Practices will be provided a set of 100 patient exit cards at each assessment interval. As a baseline, practices will be provided 50 cards in the run-in phase. At each practice, exit cards will be distributed by office staff to consecutive patients (19 and over). Eligible patients will be adults who have completed their visit. In a pilot study for DTC.Net, patients were asked to record the time required to complete the pilot survey. The average time to complete was two minutes and ranged from one to three. The exit cards are administered while the patient is awaiting follow-up instructions and completing payment. A brief statement is included explaining the study, indicating that participation is voluntary, and that their responses will not influence the care that they receive. Importantly, participation is anonymous and no patient identifiers will be included on the Exit Cards. This recruitment is solely to assess provider performance and no patient follow-up is needed.

Each patient is provided a pen to help complete the survey and as a gift. Patients place completed exit cards in an accompanying envelope and then deposit in a sealed collection box. If a patient is not interested in completing the exit card, they write “declined” and return the card to the box. When all exit cards are distributed, the practice returns the collection box to our coordinating center. For each set of 100 exit cards, we estimate 20 to 25 tobacco users will be identified.

The exit card will contain brief questions used to assess whether the patient was a tobacco user and whether the provider **Referred** the patient. We will also assess age, gender, other components of the 5A’s, and stage of change: a part of the Transtheoretical Model of behavior change.

We will provide a small reimbursement for data collection (visa debit cards) to the office staff as remuneration for their assistance in distributing exit cards (see budget justification). As discussed in our preliminary data above, from 19,000 exit cards distributed for DTC.Net the response rate has been over 85%.

We had considered collecting exit cards on only smokers, but 1) prior experience with these cards indicates that any instructions other than simply consecutive patients dramatically reduces practices’ ability to complete the data collection and 2) in addition to assessing Refer, we also want to assess rates of Ask (screening for smoking by staff) and Advise (staff advising tobacco users to quit). For the assessment of Ask, we need both smokers and non-smokers.

**Patient Recruitment Part 2: Website** - We will recruit through the website in two layers. First, as they enter the website, patients will be informed that we will monitor use of the website and that reports of total number of uses will be returned to their providers. All patients will be asked to identify their provider (using a unique ID) so that we can provide feedback reports to providers and have data for hypothesis 2. Second, patients will be asked to agree to a six-month follow-up telephone survey similar to the patient exit cards (hypothesis 3). Those who agree will be asked to provide contact information including a phone number and name, again through a SSL online form. Because we want to have as many patients participate in Decide2Quit as possible, we will not require agreement to follow-up as a prerequisite to using the site.

	Intervention			Control		
	Total N	N	%	Total N	n	%
Start with 1,000 patient visits						
Total Smokers	1000	200	20%	1000	200	20%
% of Smokers Referred	200	48	24%	200	24	12%
% of Smokers Referred who GO	48	19	40%	24	4.8	20%
% of Smokers that GO who QUIT	19	3	15%	5	0.5	10%

Because not all smokers will be interested or ready to be referred, we have estimated the number of smokers per practice that will participate in the website over time. We estimated 1,000 visits by unique patients per year to the dental practice. Based on tobacco use prevalence in DTC.Net, approximately 20% of the patients will be smokers. To be conservative, we assume that we will have only two providers per practice actively participating in the intervention. Using these numbers, we have estimated the number that will

Principal Investigator/Program Director (Last, First, Middle): DPBRN c/o [name] participate per practice yearly (Table 8). In many practices, there will likely be more than one hygienist referring. Thus, the actual number referred may be proportionately higher in each arm.

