### 2. Patients’ Portal - Decide2Quit:

The Decide2Quit patient intervention website will include previous self-management content developed and evaluated for “Smoking Coach” (current HI-QUIT control website) and will also undergo considerable augmentation to be integrated into the microsystem. The major augmentation to transform the “Smoking Coach” into Decide2Quit is the database linkages with Refer2Quit (provider portal), the automated email messaging, the administrative portal for content management. We will also add new content including the latest pharmacotherapies, new “How to Talk to Your Provider” content, and additional risk

Principal Investigator/Program Director (Last, First, Middle): DPBRN c/o [name]

calculators. We envision Decide2Quit as a portal to smoking cessation information. Thus, we will add links to other high-quality web-based information on smoking cessation such as **smokefree.gov**, and will provide links to community resources, heavily emphasizing the additional benefit of quitlines (1-800-Quit-Now).

[figure not shown]
**Help Desk:** In addition to the technical aspects of the system, our recruitment and retention staff will serve as a “help desk.” The help desk will respond to provider and patient questions, but will also be **pro-active**. Interventions that are easier to integrate into the processes of the clinical microsystem are more likely to be adopted. Top-Down, one-size-fits-all interventions often are not well integrated. We plan to be flexible and provide support to intervention microsystems in their implementation of HI-QUIT. Thus, we will work with offices to understand how each practice can best implement active referrals.

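### Randomising practices in fixed, stated blocks of six, while recruitment staff also run the intervention-only help desk, is an avoidable weakness in allocation concealment

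*Protocol*

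**What the plan says.** Protocol section D5 describes the allocation. When a provider agrees online, the server's program will "randomize their practice to the control or intervention arms in blocks of six to assure roughly equal numbers". The unit is the practice: "the first provider who logs on will determine the randomization status for all providers and staff within the entire practice". The target is given as "We plan to recruit 80 general dentistry practices (40 total practices per arm". The section mentions no strata, no variation in block size, no withholding of the block size and no masking of study staff.

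Two other places bear on who can know what. Section D2, under the help desk, says that "our recruitment and retention staff will serve as a" help desk. It also says the desk will be proactive and will "provide support to intervention microsystems in their implementation of HI-QUIT". Section D3 lists the help desk first among the things control practices do not get. Before randomisation, in step 4 of provider recruitment (section D5), the same group is in touch with practices: "Our recruitment coordinators will call the contact person at the practice who is responsible for data collection to answer any questions".

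**The concern.** With a fixed block of six and equal allocation, anyone who has followed the current block knows the remaining assignments once one arm has had its three. A server hides the list, but it cannot prevent this inference.

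The trial cannot be blinded at practice level. The recruitment staff support intervention practices directly, and before randomisation they also have information on each practice: the interest survey records level of interest (Table 9), and run-in exit cards are returned to the study. Assignment waits for the first click by a provider, and about 100 interested practices are expected to yield 80 randomised. If the next slot could be foreseen, the speed with which a practice is brought through run-in to log-on could, even without intent, come to depend on that slot. With practices as the randomised units, a tilt of keener practices towards one arm would matter most for referral (H1).

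**Working it through.** The protocol gives no predictability figure, so there is none to reproduce. The check asks how much a fully informed observer could foresee.

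**Inputs.** Block size 6, allocation 1:1 (so 3 + 3 per block), one sequence, 80 practices, all from section D5. Assumption not in the protocol: the observer knows every earlier assignment, in order.

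**Forced assignments in one block.** There are C(6,3) = 20 equally likely blocks. An assignment is forced when one arm already has three.
- 4th place: forced if the first three are all alike, 2/20 = 10%.
- 5th place: forced if the first four split 3 to 1, 8/20 = 40%.
- 6th place: always forced, 100%.

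Expected number = 0.1 + 0.4 + 1.0 = 1.5 of 6, or 25%. The closed form for a block of 2m agrees: 2m/(m + 1) = 6/4 = 1.5.

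**Over 80 practices.** 80 = 13 × 6 + 2, and the last two places are never forced. 13 × 1.5 = 19.5, and 19.5/80 = 24.4%.

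**Best guess.** Guess the arm that is behind in the block, or toss a coin when level. The probabilities of being right at places 1 to 6 are 0.5, 0.6, 0.6, 0.7, 0.7 and 1.0, which sum to 4.1 of 6 = 68.3%. Over 80 practices: (13 × 4.1 + 0.5 + 0.6)/80 = 54.4/80 = 68.0%.

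**Alternatives on the same measures.**

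| Scheme | Forced | Best guess right |
|---|---|---|
| Fixed 6, over 80 practices | 24.4% | 68.0% |
| Fixed 8, per block | 20.0% | 66.6% |
| Fixed 10, per block | 16.7% | 65.3% |
| Sizes 2, 4, 6, 8 mixed equally often | depends on what the observer can infer about block size | 68.8% |
| Coin toss, maximum imbalance 3, over 80 practices | 16.1% | 58.1% |

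For the mixed blocks, the expected correct guesses are 1.5, 2.83, 4.1 and 5.33, together 13.76 of 20 = 68.8%. The guess uses only running totals, which are level at the end of every block, so hiding the block size does not reduce it.

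For the imbalance limit, each assignment is a fair toss unless the arms differ by 3, when the next one must go to the smaller arm. Starting level, the expected number of forced assignments over 80 is 12.9, or 16.1%. The best guess is then right 0.5 + 0.5 × 0.161 = 58.1% of the time. A limit of 3 is the largest gap that blocks of six can themselves reach.

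**Final balance at 80.** Fixed blocks of six end 40/40 with probability 0.6 and 41/39 (either way) with probability 0.4. The limit of 3 ends 40/40 with probability 1/3 and 41/39 with probability 2/3. A difference of 3 can arise only if the total is odd.

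**The case against.** The case for leaving this alone is substantial.

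- **Knowledge of the sequence is not shown.** Nothing says staff see assignments as they occur. The help desk reveals which practices are in the intervention arm, perhaps with delay; control status and order must be inferred. This stands, and it is why the quarter is a worst case.
- **The route is narrow.** The server assigns only after consent and run-in, and staff cannot override it. Section D5 describes the e-mails as broadcast to everyone who agreed to contact, and the coordinator calls as answering run-in questions rather than prompting log-on. With 80 practices enrolled over months 6 to 10, about 16 a month, steering one practice into one slot would be hard. This also stands. What remains is the timing of run-in completion and log-on.
- **Baseline data exist.** Level of interest, practice structure, patient volume and pre-intervention counselling are collected (Table 9), and the H1 models allow adjustment for such variables. That could remove part of an imbalance, but not unmeasured keenness.

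Two stronger readings are tempting. A reader might infer that staff can in fact predict a quarter of assignments from a published block size. The documents show only that the size is written in the protocol, not that it was public during enrolment or that staff track the sequence. A reader might also infer, citing the practice ICC of 0.15, that H1 is biased and that the bias passes to H2 and H3. That ICC was estimated in the earlier dental trial for advice to quit and is only assumed equal for referral (section D10). It does not measure selection bias, and no bias can be quantified from the protocol.

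**Conclusion.** The point holds as a weakness in allocation concealment that can be avoided. The protocol fixes one block size, describes no masking of staff, and gives the recruiting team a role that shows them which practices are in the intervention arm. Under full knowledge of earlier assignments, 24.4% of the 80 would be certain in advance and about 68% could be guessed correctly. With partial or delayed knowledge both figures would be lower, by an amount the protocol does not allow one to compute. This is predictability with a limited route to selection; bias in H1, H2 or H3 is not demonstrated. It merits a change because the change is small, not because the trial is shown to be compromised.

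**What to change.** In the existing server program, replace the fixed blocks of six with unblocked allocation under a maximum imbalance limit, for example a difference of 3 practices. Keep the limit and the method's settings out of documents that recruitment staff see. Send log-on invitations automatically at a fixed interval after a practice's run-in cards are received, so that timing does not rest on staff judgement.

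Randomly varying block sizes are a weaker alternative. They reduce certainty if the sizes are withheld, but not the success of the best guess, and very small blocks should be left out because a block of 2 is guessed correctly 75% of the time. A larger fixed block is also only a partial answer, since size 10 still forces 16.7% and leaves the best guess at 65.3%.

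The cost is a small programming change before activation and a final arm difference of up to 2 practices at exactly 80, or 3 if the total is odd. That still meets the stated aim of roughly equal numbers and needs no change to the sample size.
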